Hypothesis 1: Greater CB WML volume is associated with a) reduced resting-state connectivity of frontal, temporal, and cingulate regions and b) deficits in attention, memory and processing speed.

Hypothesis 2: Greater UF WML volume is associated with a) reduced resting state functional connectivity between frontocingulate and medial temporal regions, and b) greater depression severity and negativity bias.

Exploratory Hypothesis: Greater CB WML volume is associated with failure of anterior and posterior DMN nodes to deactivate during attentional components of the fMRI task. Greater UF WML volume is associated with greater medial temporal reactivity during affective components of the fMRI task.

Specific Aim 2: To determine whether deficits in tract structural / functional connectivity predict nonremission to antidepressant treatments and if these relationships vary based on antidepressant mechanism of action.

Hypothesis 3: Nonremission to escitalopram will be predicted by: a) greater WML volume in the CB and UF, and b) reduced resting functional connectivity between structures connected by the CB and UF. Greater WML severity and reduced functional connectivity in these tracts will not significantly predict response to placebo.

Hypothesis 4: Nonremission to bupropion will be predicted by a) greater WML volume in the UF but not CB, and b) reduced resting functional connectivity deficits between structures connected by the UF but not CB.

Exploratory Aims: **Expl. Aim 1)** To determine if specific cognitive measures may serve as markers of focal tract WML damage. **Expl. Aim 2)** To use whole-brain multimodal imaging approaches to examine how connectivity differences in other brain regions may also predict nonremission to antidepressants.

For exploratory analyses, we will also recruit 30 elders with no psychiatric history. Data from this population will help us understand whether our neural and cognitive findings in depression represent differences from what is seen in healthy aging, or whether our observations in depressed elders are within the range of normal aging. This will be important for data interpretation and planning for future projects.

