maladaptive cognitive processes (61,65). In MDD we observe a dissociation between anterior and posterior DMN nodes (66) while within-node functional connectivity is increased (38,46,63,64). As reduced functional connectivity is related to altered CB structure (67,68), we propose that WMLs in the CB adjacent to the cingulate gyrus may disrupt communication between DMN nodes. This would impair anterior-posterior connectivity, resulting in difficulty coordinating deactivation of the DMN during tasks (61). This contributes to deficits in **attention** (69,70) and **processing speed** (59,71-73), deficits associated with poor antidepressant response (21,57). *Additionally*, damage to the CB in the region of the hippocampus may have further effects. WMLs in this region may disrupt hippocampus-posterior cingulate connectivity (31,47,74) resulting in poorer episodic memory performance (75-77). This results in **episodic memory deficits** that are also associated with poor LLD antidepressant responses (21) (Figure 2.c).

3.4. Antidepressants with different mechanisms of action: Antidepressant treatment changes brain metabolism (78-82). However, antidepressants with different mechanisms of action have different effects on neural circuit connectivity (83,84) or neural activity during tasks (85,86).

The relationship between neural circuit deficits and the antidepressant response may *depend on the drug's specific mechanism of action*. We hypothesize that tract damage predicts nonresponse to antidepressants that affect neurotransmitter systems projecting through that tract. Serotonergic neurons project widely through the CB (87), but also to the orbitofrontal cortex and medial temporal lobe (88-90), suggesting UF involvement. Noradrenergic projections largely overlap with serotonergic innervation (91), including CB projections (92). In contrast, dopaminergic neurons have discrete pathways (93-96). Dopaminergic mesocortical and mesolimbic fibers may pass through the UF (97), but compared to serotonin or norepinephrine, have less CB projections (98). *Thus drugs affecting serotonin and norepinephrine may require intact connectivity in both the CB and UF, while dopaminergic agents may depend less on the CB.*

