9.4. Phase 2: Bupropion XL: We selected bupropion due to its distinct mechanism of action: a norepinephrine /dopamine reuptake inhibitor with no effect on serotonin (116,117). Bupropion is safe and effective in elderly populations (118-120). Subjects will receive open-label bupropion XL starting at 150mg daily. If tolerated, after 1-2 weeks it will be increased to 300mg daily. The dose may be further increased to the maximum of 450mg daily at week 4; this dose will be reduced if needed for tolerability. Subjects not tolerating the 300mg dose will be withdrawn.

Table 1. Cognitive Domains & Tasks (21)

Episodic Memory (Alpha = 0.76)
• Word List recall; Logical memory; Constructional praxis; Benton Visual Retention Test
Executive Function (Alpha = 0.73)
• Verbal Fluency; Trail Making Test, Part B; Stroop, color-word interference; Mattis DRS, Initiation-Perseveration subscale; Wisconsin Card Sorting Test
Language Processing (Alpha = 0.62)
• Shipley Vocabulary Test; Boston Naming Test; Stroop, word reading
Processing Speed (Alpha = 0.69)
• Symbol-digit Modality Test; Stroop, color naming; Trail Making Test, Part A
Working Memory (Alpha = 0.68)
• Digit Span, forward; Digit Span, backwards; Ascending Digits

Although bupropion is often used for augmentation (121-123) for Phase 2 we decided to use it as *monotherapy*. This is supported by STAR*D data (124) that found no clear preference for augmentation versus switch strategies (125). This will simplify interpretation of Aim 2 data.

Bupropion xl may be obtained through the Vanderbilt investigational pharmacy and provided to subjects. Alternatively, the study doctor will provide a prescription and they may obtain it through their regular pharmacy. In this case, they will be instructed to save their receipts so they can be reimbursed for their cost.

9.5. End of study medication procedures: For subjects who wish to continue on their end-of-study drug, we will provide prescriptions and assist with follow-up. If they do not wish to continue on study drug, we will make referrals and work with that provider to safely taper the study drug. See Human Subjects for more detail.

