We will use a similar approach for Exploratory Aim 1, where we examine how cognitive test performance may serve as a marker of WML tract damage. Including the previous covariates plus education, cognitive test results will be on the independent side with tract WML values on the dependent side.

Data from nondepressed elders will be integrated into the above analyses. We will test for group differences in the neuroimaging and cognitive measures described above. We will also include a group variable (depressed or not depressed) in analyses.

Aim 2 examines how tract measures predict remission. Following our previous approach (21), our definition of remission is MADRS ≤ 7 . Secondly, we will examine drug response (50% improvement on MADRS). Remission / response status for subjects with missing data will be estimated via multiple imputation

method assuming that dropouts are missing at random.

We will use two regression models to test for mediation while adjusting for baseline MADRS, age, sex, and vascular risk. To assess indirect effects of tract WML and FC measures as mediator variables, we will regress a potential mediator on a tract-based measure (an explanatory variable of interest). We will fit another model in which antidepressant remission or nonremission serves as outcome variable, and the potential mediator and tract-derived measure serve as covariates. The second model can be either logistic or linear regression model depending on the nature of outcome. The product of two beta coefficients corresponding to the tract-based measure in the first model and to the mediation variable in the second model will be assessed by constructing bootstrapped 95% confidence intervals (CI); statistically significant difference from zero implies that the relationship between the outcome and explanatory variable is mediated by the variable in question (127,128).

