This approach will slightly differ for each study phase. For Phase 1, models will include drug arm (placebo or escitalopram). To examine for differences in how tract impairment affects remission in each arm, we will test for interactions between drug assignment and tract integrity (WML & FC). We will explore significant interactions in individual models. For subjects entering Phase 2, we will test for differences in tract integrity (WML & FC) between those originally assigned to escitalopram and placebo. If differences are observed, in models we will control for original Phase 1 cohort assignment. In exploratory models, we will use similar approaches to test for the additional effect of cognitive domain function (Table 5) on remission. We will also use this approach for Exploratory Aim 2 when we examine the effect of connectivity deficits in other tracts.

Importantly, the relationship between connectivity and antidepressant response may not be linear. It is possible that a ‘threshold’ must be crossed in order for tract connectivity deficits to influence response (3). To properly take into account nonlinear effect of a continuous predictor variable (e.g., WML, FC) on response variable (e.g., remission or nonremission) in the models, we will employ restricted cubic splines of the predictor. Statistical significance of the nonlinear terms via F-test implies that the relationship between the two measures of interest can be nonlinear.

15.1. Sample Size and Statistical Power:

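### Hypothesis 4 claims that UF but not CB predicts bupropion nonremission, but the Aim 2 plan has no UF–CB comparison and no criterion for calling CB unrelated

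*Combined protocol and SAP*

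**What the plan says.** Section 2.0, Hypothesis 4, predicts a dissociation within the bupropion phase: "Nonremission to bupropion will be predicted by a) greater WML volume in the UF but not CB". Part b repeats it for resting FC.

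The Aim 2 analysis is in section 15.0. It fits two regressions "while adjusting for baseline MADRS, age, sex, and vascular risk". In the outcome model "the potential mediator and tract-derived measure serve as covariates". The product of coefficients gets a bootstrapped 95% CI, and a "statistically significant difference from zero implies that the relationship between the outcome and explanatory variable is mediated" by the variable in question. Three other procedures are described:

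- For Phase 1, an interaction between drug assignment and tract integrity.
- For Phase 2, a check whether tract measures differ between the original arms: "If differences are observed, in models we will control for original Phase 1 cohort assignment".
- For nonlinearity, "we will employ restricted cubic splines of the predictor", with a test of the nonlinear terms.

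The Aim 2 power text in section 15.1 is written for Phase 1. It gives no Phase 2 sample size or power.

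**The concern.** None of these procedures sets UF against CB. The arm-by-tract interaction compares escitalopram with placebo in Phase 1 and serves Hypothesis 3. Phase 2 has a single open-label drug, so that interaction cannot answer Hypothesis 4. No margin or other criterion says how small a CB effect must be.

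Without such a criterion, the natural reading of Phase 2 is that UF reached significance and CB did not. Two estimates can fall on opposite sides of a threshold without differing from each other, and a nonsignificant estimate in a small sample is compatible with a sizeable effect.

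The protocol's own theory makes a CB effect plausible. Section 3.4 says that "drugs affecting serotonin and norepinephrine may require intact connectivity in both the CB and UF, while dopaminergic agents may depend less on the CB", and section 9.4 describes bupropion as "a norepinephrine /dopamine reuptake inhibitor with no effect on serotonin". The dopamine half of that argument is also one of degree. Since the background section hopes that circuit findings may guide the choice of antidepressant, a false claim of tract specificity would matter.

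**Working it through.** **The plan's own figure.** There is none for Hypothesis 4. The nearest is the Phase 1 detectable effect of 0.45 (called a log hazard ratio, although the model is logistic) at N = 130, base nonremission 0.36 and covariate share 10%. No power is attached to it. Read as a log odds ratio (OR) per SD, √(130 × 0.36 × 0.64 × 0.9) = 5.19; 5.19 × 0.45 − 1.96 = 0.38, a two-sided power of about 65%. There is nothing to match it with, so 0.45 is used below only as a scale.

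**Inputs.** From the documents: 0.36 × 130 = 47 as a low Phase 2 n. For the high n, section 15.1 wants comparable numbers on each active drug, and 130 × 2/3 = 87. Assumed, because the documents do not give them: UF–CB correlation ρ = 0.5, Phase 2 nonremission p = 0.5, two-sided 5% tests.

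**Large-sample check, both tracts in one model.** Let I = n·p(1−p)·0.9. Then SE(each) = 1/√(I(1−ρ²)) and SE(UF−CB) = √(2/(I(1−ρ))).

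- n = 47: I = 10.575, SE(each) = 0.355, SE(UF−CB) = 0.615. A true CB effect of 0.45 gives z = 1.27 and is nonsignificant in about 75% of trials. Contrast power for 0.45 versus 0: z = 0.73, about 11%.
- n = 87: I = 19.575, SE(each) = 0.261, SE(UF−CB) = 0.452. The same quantities are z = 1.72, about 59%, and z = 1.00, about 17%.

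**Simulation.** Generic logistic models with four null covariates and Phase 1 arm, Wald tests, 5,000 trials per cell. The pattern means UF significant in the predicted direction and CB not significant.

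| True log OR per SD (UF, CB) | Result | n=47 | n=60 | n=87 |
|---|---|---|---|---|
| 0.45, 0.45 | pattern, one tract per model | 17.5% | 16.9% | 12.6% |
| | pattern, joint model | 19.4% | 23.9% | 30.4% |
| | contrast favours UF | 2.6% | 2.7% | 2.4% |
| | CB nonsignificant, joint model | 78.2% | 73.0% | 62.6% |
| 0.7, 0.7 | pattern, one tract per model | 12.6% | 8.0% | 2.0% |
| | pattern, joint model | 29.4% | 31.8% | 29.0% |
| | contrast favours UF | 2.5% | 2.5% | 2.7% |
| 0.45, 0 | pattern, one tract per model | 22.8% | 27.6% | 37.4% |
| | contrast favours UF | 11.4% | 12.3% | 17.0% |
| 1.0, 0 | pattern, one tract per model | 55.5% | 57.0% | 50.2% |
| | pattern, joint model | 64.3% | 77.2% | 88.9% |
| | contrast favours UF | 28.9% | 37.5% | 51.4% |

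Repeat runs move these by a few points (the last cell reaches about 54%). Over correlations 0.3–0.7 and nonremission 36–64%, with equal effects of 0.45–0.7, the false pattern ranges over 0.4–21% (one tract per model) and 14–36% (joint), and the contrast stays at 2–3%.

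**Why a true Hypothesis 4 is missed.** With UF 0.45, CB 0 and one tract per model, UF is nonsignificant in 72/63/51% of trials (n = 47/60/87) and both tracts are significant in 7/9/13%. Low power therefore accounts for 72/79 = 91%, 63/72 = 88% and 51/64 = 80% of the misses. CB picking up UF's effect through their correlation is the main cause at every n only for a large effect, about 1.0.

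**Can CB be bounded?** With CB truly 0 and UF 0.45–1.0, the 95% CI half-width for CB in the joint model is 0.84–0.92 (n = 47), 0.70–0.76 (n = 60) and 0.55–0.60 (n = 87), all above 0.45. An equivalence bound of ±0.45 is met in 0–3% of trials.

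**The case against.** The rule about difference from zero is written only for the mediated product. The text sets no rule for direct tract effects and does not say whether UF and CB share a model; Aim 1 does enter WML values jointly. Both readings used above are therefore inferences. This stands. The closest reading is one tract per model, since one tract-derived measure and one mediator are described and the other tract is not among the listed covariates. The gap is present either way, and the joint model without a contrast gives the false pattern more often. Hypothesis 3 itself words its placebo prediction in terms of not significantly predicting, so reading nonsignificance as a finding is not foreign to the plan.

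The simulation also omits the planned mediator, bootstrap and multiple imputation, and it always includes Phase 1 arm, which the plan makes conditional. This stands too. A reader might infer that 12–30% is the error rate of the planned analysis. The documents do not support that: the percentages illustrate a generic model with assumed inputs.

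The contrast confirms a true Hypothesis 4 less often than the significance pattern does at most sizes. That is correct. It is a reason to restrict the claim, because the pattern's higher hit rate comes with false dissociations.

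**Conclusion.** The omission is certain from the text: Hypothesis 4 asserts a dissociation, and section 15.0 provides neither a UF–CB comparison nor a criterion for no CB effect. Its size is illustrative and rests on the assumed Phase 2 n, correlation and event rate. At equal effects of 0.45, a false UF-but-not-CB pattern appears in about 12–18% of trials (one tract per model) or 19–30% (joint), against 2–3% for the contrast. A real CB effect of 0.45 is nonsignificant in about 62–78% of joint models. At 0.7 and n = 87 with one tract per model there is no excess over the contrast (2.0% versus 2.7%).

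Two stronger readings are not supported. One is that a true Hypothesis 4 would usually be missed because CB borrows UF's signal; at 0.45, most misses are simply low power. The other is that the within-bupropion contrast would establish that mechanism of action matters. It does not test whether the CB effect differs between escitalopram and bupropion.

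**What to change.** In the SAP:

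1. Prespecify one standardised summary per tract for WML and one for FC. The preliminary-data table lists CB by segment and side, so the choice is otherwise open.
2. In Phase 2, fit the UF and CB linear terms together. Report both coefficients and β_UF − β_CB with 95% CIs, for WML and for FC, and the bootstrapped UF–CB difference in indirect effects. Keep the splines as a sensitivity analysis.
3. State that a nonsignificant CB coefficient will not be read as no effect, and label the absence of a CB effect descriptive. At these sample sizes an equivalence claim is unrealistic.
4. State that Hypothesis 4 is exploratory and aimed at estimation.

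The cost is analysis work only; data collection, sample size and treatment are unchanged. The limits to disclose are:

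- Contrast power is low: about 11–17% for 0.45 versus 0, and 29–54% for 1.0 versus 0.
- At n = 47 with 50% events, the joint model has seven terms (two tracts, four covariates, arm) for about 23 events, so it is imprecise.
- A contrast per SD depends on each measure's spread and reliability.
- The cross-drug question stays untested.

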Aim 1: From our published report (129) correlations of the FC of the PFC with the amygdala and the hippocampus were in the range of 0.52 to 0.55. A sample of 130 subjects, will have > 90% statistical power for associations ≥ 0.30 (two-tailed $\alpha = 0.05$). However, our primary approach to the analysis of Aim 1 will use canonical correlation with no known powering algorithms; sample size and effect estimates are used to guide the appropriateness. Using the multiple regression approach (single dependent) as a conservative estimate, a sample size of 130 achieves 83% statistical power to detect an R^2 as small as 0.06 (standardized beta = 0.20, 6% shared variance) attributed to the association of WML with a significance level (alpha) of 0.05 after adjusting for other proposed covariates. These calculations assume that the variables for which we are adjusting have an R^2 of 0.10 (10%) (130). We suspect that the control variables will have a higher inter-correlation value, thus increasing our power for testing the effect of a single variable.

Aim 2: The study includes a placebo arm to identify effects specific to an active depressant while having a comparable number of subjects receiving each active drug. Powering the study for Phase 1, Table 2 presents estimates for our proposed sample size using unadjusted effects of low vs. high WML values on the respective

outcomes of interest found in our preliminary data. The logistic regression approach allows for the testing of effects adjusted for known covariates. Using this approach, assuming a base non-remittance rate of 0.36 (36%), a sample size of 130 will enable us to detect a log hazard ratio as small as 0.45 for a specific measure. We conservatively included an assumption that covariates would account to up to 10% share of the effect on nonremission. If that value is less, our statistical power will increase for the same hazard ratio. Using high vs. low tract WML volume as an example, after controlling for other effects, our sample will enable us to detect an effect on the likelihood of non-remittance of at least 25% (high WML vs. low WML, $0.45 / 0.36 = 1.25$ or 25% increase). Continuous as well as nonlinear operationalization of effects will be examined.

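### For the lesion associations in Aim 1, the plan pools nondepressed with depressed elders and adds a group variable but no group-by-lesion term, so it cannot show whether those associations differ from healthy aging

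*Combined protocol and SAP*

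**What the plan says.** The last paragraph of Section 2.0 gives the nondepressed cohort an exploratory purpose in two halves. The first half asks "whether our neural and cognitive findings in depression represent differences from what is seen in healthy aging". The second half concerns levels; it asks "whether our observations in depressed elders are within the range of normal aging".

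The Aim 1 hypotheses in the same section are mostly stated as associations. Hypothesis 1 begins "Greater CB WML volume is associated with a) reduced resting-state connectivity of frontal, temporal, and cingulate regions" and goes on to attention, memory and processing speed. Hypothesis 2a links uncinate lesion volume with connectivity, and the exploratory hypothesis links lesion volume with task activation.

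The analysis of the nondepressed data is three sentences in Section 15.0, placed after the Aim 1 and Exploratory Aim 1 canonical correlation analyses:
- The first pools the data: "Data from nondepressed elders will be integrated into the above analyses".
- The second is a comparison of levels: depressed and nondepressed elders are tested against each other on the imaging and cognitive variables.
- The third concerns the models: "We will also include a group variable (depressed or not depressed) in analyses".

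For Aim 2, the same section does name an interaction: "we will test for interactions between drug assignment and tract integrity (WML & FC". No corresponding group-by-WML term, and no group-specific fit, is stated for Aim 1.

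**The concern.** Whether an association found in depressed elders differs from healthy aging is a question about slopes: does connectivity or cognition fall more steeply with lesion volume in one group than in the other? A comparison of group means does not address this. A group variable in a pooled model does not either, because it moves the level of the fit and leaves one set of WML weights for everyone.

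Two things are at stake. First, the data cannot separate a lesion effect common to older adults from one specific to depression, although the controls are placed inside the models where that question arises. Second, if the pooled fit is read as the Aim 1 result, it is no longer an estimate for depressed elders, and it is diluted if lesions matter less in the controls.

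**Working it through.** **Inputs from the documents.** 130 depressed participants and two-sided alpha 0.05 (Section 15.1). Nondepressed participants: 30 (Section 2.0) or 40 with MRI data (Section 4.0). These two figures need reconciling, so both are used here.

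**Assumptions, not in the documents.** WML slope -0.30 SD per SD in depressed elders and 0 in nondepressed elders; WML SD equal in the two groups unless stated. Ordinary regression with one outcome stands in for canonical correlation.

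**1. The plan's own figure.** Section 15.1 states: "A sample of 130 subjects, will have > 90% statistical power for associations" of at least 0.30. By Fisher's z, atanh(0.30) × √(130 − 3) = 0.3095 × 11.27 = 3.488, and Φ(3.488 − 1.96) = 93.7%. The figure reproduces. It concerns the depressed cohort alone; no power or precision is given for the group comparison.

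**2. What the pooled model estimates.** With equal WML variance, the common slope is the sample-size-weighted average of the two slopes:
- 40 controls: (130 × −0.30 + 40 × 0) / 170 = −0.229
- 30 controls: (130 × −0.30 + 30 × 0) / 160 = −0.244

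Simulation (4,000 data sets per scenario) gave −0.231 and −0.245.

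**3. What the group term shows.** Simulation with 130 + 40, three covariates, and no mean difference between groups at average WML:

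| Control slope | Common slope | Common slope significant | Group term significant |
|---|---|---|---|
| −0.30 | −0.30 | 98% | about 4–5% |
| 0 | −0.23 | 86% | about 5–6% |

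This depends on the two lines crossing at average WML. Suppose instead that they meet at zero lesion volume. The gap at average WML is then 0.30 × (WML mean/SD), with standard error √(1/130 + 1/40) = 0.181 for residual SD 1:
- mean/SD 0.5: 0.15/0.181 = 0.83, power 13%
- mean/SD 1.0: 0.30/0.181 = 1.66, power 38%
- mean/SD 1.5: 0.45/0.181 = 2.49, power 70%

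A simulation with skewed WML gave 13%, 42% and 77%. The group term can therefore react to a slope difference, but a constant level shift with equal slopes can produce the same significant term. It does not identify which of the two is present.

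**4. What a group-by-WML term would give.** The standard error of the slope difference is √[(1 − 0.30²)/128 + 1/(n − 2)]:
- n = 40: √(0.00711 + 0.02632) = 0.183; 95% half-width 1.96 × 0.183 = 0.36; power Φ(0.30/0.183 − 1.96) = 37.5%
- n = 30: √(0.00711 + 0.03571) = 0.207; 95% half-width 0.41; power 30.5%

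Simulation recovers the difference without bias (−0.30). With 40 controls the half-width is 0.35 and power 38–41%; with 30 controls power is 31–33%. If WML SD in controls is 0.7 of that in patients, the half-width with 40 controls is about 0.47 and power about 24–25%.

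The slope difference detectable with 80% power, taking residual SD 1, is 2.80 × √(1/128 + 1/38) = 0.52 with 40 controls and 2.80 × √(1/128 + 1/28) = 0.58 with 30.

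**The case against.** The strongest reply is that the stated purpose may concern levels only. Section 2.0 refers to findings in general, not to lesion associations, and its second half is plainly about levels. On that reading the planned group tests answer the question. This stands in part: the slope reading is inferred. But Section 15.0 places the controls inside the association models, so some question about associations seems intended, and none can be answered as written.

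A reader might infer that a group main effect is all the plan offers. It is not; tests of group differences in the measures are planned too, and they serve the level question. Nor does the text rule out an interaction. It is silent, and a term added later would be a post hoc choice.

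A reader might also infer that a depression-specific lesion effect and an ordinary aging effect would always give the same planned output. That holds only if the groups' lines cross at average WML. The documents do not make that assumption; Sections 3.2 and 3.2.a cite group differences in lesion severity and, in some studies, connectivity. What remains is that a significant group term cannot tell a slope difference from a level shift.

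Two further points stand. Canonical correlation has no single common slope, so the figures are illustrative. And Sections 2.0 and 15.1 frame Aim 1 around 130 depressed elders; if H1 and H2 are estimated in them alone, dilution does not reach those results. The plan should say which applies.

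**Conclusion.** The point holds in a limited form. The level half of the cohort's purpose is covered. For the findings that are WML associations (H1, H2a and the exploratory task hypothesis), the analysis as written estimates one association common to both groups and cannot show whether it differs from healthy aging.

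Under the assumed slopes, pooling moves the estimate from −0.30 to about −0.23 with 40 controls or −0.24 with 30. These sizes rest on the assumed slopes, equal WML variance in the two groups, and a single-outcome regression in place of the canonical model. That the association is common to both groups follows from the model as described and needs none of these assumptions.

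The cohort is exploratory, and no treatment comparison or Aim 2 result is affected. This is an inexpensive improvement to an exploratory analysis, not a flaw in the trial's main conclusions.

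**What to change.** In the Section 15.0 paragraph on nondepressed elders:
1. Keep the group comparisons of levels.
2. State that H1 and H2 are estimated in depressed participants.
3. Replace the general statement about a group variable with an exploratory model for each WML–connectivity and WML–cognition association: regression on group, tract WML, group × tract WML, age, sex and vascular risk. Report the WML slope in each group and the slope difference with its 95% CI.
4. State that only the slope difference supports a claim that an association differs from healthy aging, and that a non-significant difference is not read as similarity.
5. Reconcile the control numbers in Sections 2.0 and 4.0, and state the expected precision.

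The cost is a few sentences and one model term, with no new data. The downside is imprecision. With 40 controls the interval extends about 0.35 to 0.47 SD per SD either side of the estimate, which is wider than the assumed difference of 0.30, and with 30 controls it is wider again. The result will often be inconclusive and should be presented as an estimate, not a pass/fail test.
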